1.2.2 Summary of human experience with enzalutamide (MDV3100)

The pharmacokinetics (PK), tolerability, and antitumor activity of MDV3100 were first studied in a multi-center, open-label, first-in-human, dose-escalation study of MDV3100 in 140 patients with castration-resistant prostate cancer (S-3100-1-01).¹⁰ Patients who were chemotherapy-naïve or who had previously failed docetaxel-based chemotherapy were treated with MDV3100 at doses of 30 to 600 mg/day until disease progression or intolerable side effects developed.

MDV3100 was absorbed rapidly after oral administration, with the time to maximum plasma concentration (tmax) after a single dose typically occurring at 1 hour postdose. No major deviations from dose proportionality were observed over the dose range 30 to 600 mg. Due to the long t1/2 (~ 5.8 days), it took approximately 1 month to reach steady state. With daily oral administration MDV3100 accumulation was observed at steady

state with an 8.3-fold higher exposure (steady-state area under the curve [AUC]) relative to a single dose. Based on the mean peak-to-trough ratio, the average difference between the peak (Cmax) and trough (minimum plasma concentration [Cmin]) concentrations was $\leq 25\%$. As a result of the low daily fluctuations, plasma profiles at steady-state resembled a constant infusion. The Cmin values in individual patients remained constant beyond Day 28 of chronic therapy, suggesting time-linear PK once steady state was achieved.

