The maximum tolerated dose was determined to be 240 mg daily. MDV3100 demonstrated antitumor activity across endpoints in patients both with and without previous exposure to chemotherapy. The antitumor activity endpoints included prostate-specific antigen (PSA) reduction from baseline, median time to PSA progression, responses on imaging, and circulating tumor cell conversion from unfavorable to favorable counts. Three potential MDV3100-associated toxicities were identified in this study: fatigue, rash, and seizure. Three seizures (2 witnessed, 1 unwitnessed) occurred in this study at doses of 360, 480, and600 mg/day, and were reported between 26 and 48 days after initiation of MDV3100. After review of all data available from the S-3100-1-01 study, the optimal dose of MDV3100 for evaluation in Phase 3 clinical trials was determined to be 160 mg/day. A Phase 3, randomized, double-blind, placebo-controlled efficacy and safety study of oral MDV3100 (160 mg daily) in patients with progressive castration-resistant prostate cancer previously treated with docetaxel-based chemotherapy (CRPC2, also known as AFFIRM) was conducted in 1199 men, 800 of whom received treatment with MDV3100.¹¹

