4.0 TREATMENT PLAN

4.1 Treatment Dosage and Administration

- 4.1.1 We propose a single-institution, single-arm study of neo-adjuvant, concomitant, and adjuvant enzalutamide plus GnRH agonist with external beam radiation therapy for the treatment of patients with high-risk and locally-advanced prostate cancer.
- 4.1.2 Eligible study participants will receive treatment with enzalutamide 160 mg daily for 6 months in combination with GnRH agonist treatment. Following the initial two months of treatment with enzalutamide and GnRH agonist, radiation therapy will be administered as detailed below. GnRH agonist treatment will be continued for a total treatment duration of 24 36 months at the discretion of the treating physician in concert with the patient. Treatment will be administered on an outpatient basis.

Table 4.1 Agent	Dose	Route	Schedule
Enzalutamide	160 mg daily (four 40 mg capsules)	p.o.	Daily for 6 months
Leuprolide acetate	22.5 mg every 3 months	IM	Every 3 or 6 months (depending on dosage
	or		form used) for a total treatment duration of
	45 mg every 6 months		24-36 months

A study medication diary will be provided to each subject in which daily oral selfadministration of enzalutamide will be documented. If a dose is missed, enzalutamide should be resumed the next day at the established daily dose of 160 mg. A vomited dose should not be replaced.

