4.2 Toxicities and Dosing Delays/Dose Modifications

Any subject who receives treatment on this protocol will be evaluable for toxicity. Each patient will be assessed for the development of toxicity according to the Time and Events table (Table 5.4). Toxicity will be assessed according to the NCI Common Toxicity Criteria for Adverse Events (CTCAE), version 4.0. Dose adjustments should be made according to the system showing the greatest degree of toxicity.

Enzalutamide (Xtandi, MDV3100) has been shown to be well-tolerated when used in combination with androgen deprivation (in the form of GnRH agonists or castration by orchiectomy) in completed phase I, II, and III clinical trials.

Та	ble 4.2.1 Hematological To	oxicity Dose Reductions for Enzalutamide
ANC	Platelets	Action
≥ 1,500/µL	100,000/μL	None.
1000-1499/μL	75,000-99,000/μL	 -1st Occurrence:Hold current dose until ANC ≥ 1,500/µL and platelets ≥ 100,000/µL. Do not replace missed doses. Restart next treatment at 120 mg dose. -2nd Occurrence:Hold current dose until ANC ≥ 1,500/µL and platelets ≥ 100,000/µL. Do not replace missed doses. Restart next treatment at 80 mg dose. -3rd Occurrence: Discontinue protocol therapy.
500-999/μL	50,000-74,000/μL	 -1st Occurrence:Hold current dose until ANC ≥ 1,500/µL and platelets ≥ 100,000/µL. Do not replace missed doses. Restart next treatment at 120 mg dose. -2nd Occurrence: Discontinue protocol therapy.
<500/μL	<50,000/μL	-1st Occurrence: Discontinue protocol therapy.

Table 4.2.2. Non-hematological Toxicity Dose Reductions		
NCI CTC Grade	Enzalutamide	
0-2	No change from original starting dose (with the exception of seizure)	
3-4	Hold until resolved to	
Second episode of	Hold until resolved to <grade 2,="" 80="" dose<="" mg="" reduce="" td="" then="" to=""></grade>	
grade 3 or 4 toxicity		
Third episode of	Remove subject from trial	
grade 3 or 4 toxicity		

In the randomized clinical trial of patients with docetaxel-refractory metastatic CRPC, 7 of 800 patients (0.9%) treated with enzalutamide 160 mg daily experienced a seizure. No seizures occurred in patients treated with placebo. Patients experiencing seizures were permanently discontinued from therapy and all seizures resolved. There is no clinical trial experience re-administering enzalutamide to patients who experienced seizures. Therefore, should a subject experience any seizure, enzalutamide will be discontinued and the subject removed from the trial.

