4.4.1.8. Radiation Therapy Adverse Events

All patients will be seen weekly by their treating radiation oncologist while undergoing EBRT. Any observations with respect to the following symptoms/side effects will be recorded: Bowel/rectal irritation manifesting as cramping, diarrhea, urgency, proctitis, or hematochezia, urinary frequency, urgency, dysuria, hematuria, urinary tract infection, or incontinence. CTCAE 4.0 will be used to grade all toxicities.

4.4.1.8.1. Clinical discretion may be used in managing radiotherapy-related side effects. Diarrhea/rectal frequency/urgency may be managed with diphenoxylate or loperamide. Bladder irritation may be mitigated with phenazopyridine. Urinary frequency/urgency can be managed with anticholinergic agents or alpha-blockers such as tamulosin. Erectile dysfunction can be managed with phosphodiesterase (PDE) inhibitors such as sildenafil.

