8.2.1 Return and Retention of Study Drug

Unused study drug (enzalutamide) will be documented and returned to the Simmons Comprehensive Cancer Center Pharmacy for destruction per Standard Operating Procedures

8.2.2 Subject compliance with the study agent, enzalutamide, will be monitored through use of a pill diary provided to each subject enrolled in the study. A new pill diary will be provided at every 4 week follow up visit for the duration of the administration of enzalutamide on the study.

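### Minor: the missed-dose rule in Section 4.1 fixes resumption at 160 mg, which is the wrong dose for a subject already reduced to 120 or 80 mg under Section 4.2

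*Combined protocol and SAP*

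**What the plan says.** Section 4.1 sets the regimen at 160 mg daily for 6 months, self-administered and recorded in a diary. For a missed dose it says: "If a dose is missed, enzalutamide should be resumed the next day at the established daily dose of 160 mg".

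Section 4.2 then creates subjects on lower doses:

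- Table 4.2.1 (hematological), first occurrence in either of the two middle bands: hold until recovery, then "Restart next treatment at 120 mg dose".
- Table 4.2.1, second occurrence in the milder of those bands (ANC 1000-1499/µL, platelets 75,000-99,000/µL): "Do not replace missed doses. Restart next treatment at 80 mg dose".
- Table 4.2.2 (non-hematological), second grade 3 or 4 episode: hold, then reduce to 80 mg. The cell is damaged in the text available, but the dose is legible. The cell for the first episode is cut off, so no dose is assumed for it here.

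Section 8.1 gives 160 mg as the protocol dose and does not mention reduced doses.

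**The concern.** The missed-dose sentence carries a fixed number and no exception, yet the next section assigns other doses. Section 4.2 covers the restart after a toxicity hold. It does not cover a dose forgotten later by a subject already reduced, and for that event 4.1 is the only visible instruction. In the readable rows of 4.2 doses only go down, so a return to 160 mg is never intended there.

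Applied as written, 4.1 would undo a safety reduction and put the subject back on the dose at which his first toxicity occurred. Dose reduction is the protocol's main response to toxicity short of stopping treatment, and safety and tolerability is the primary endpoint. Enzalutamide is taken at home, so a missed-dose instruction is used away from the clinic, and Section 11.4 requires conduct exactly as the approved protocol describes.

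**Working it through.** **The texts side by side**

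| Subject's assigned dose | Source | Resumption dose under 4.1 | Ratio |
|---|---|---|---|
| 160 mg | 4.1 | 160 mg | 1.00 (correct) |
| 120 mg | Table 4.2.1 | 160 mg | 160/120 = 1.33 |
| 80 mg | Tables 4.2.1 and 4.2.2 | 160 mg | 160/80 = 2.00 |

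No visible section says that 4.2 overrides the missed-dose sentence, or that the established dose means the subject's current one.

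**Effect on exposure**

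The plan has no figure of its own to reproduce. Section 1.2.2 supplies the half-life: "Due to the long t1/2 (~ 5.8 days), it took approximately 1 month to reach steady state". Assumptions: one-compartment linear kinetics, parent drug only, subject at steady state on the reduced dose when the dose is missed.

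- Elimination rate: k = ln 2 / 5.8 = 0.1195 per day, so a fraction exp(-k) = 0.887 is retained each day.
- Levels are expressed as the daily dose that would give that level at steady state. After one missed day: 80 × 0.887 = 71.0, and 120 × 0.887 = 106.5.
- After d days at 160 mg: level = 160 - (160 - start) × exp(-k d).

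| Days at 160 mg | From 80 mg (start 71.0) | From 120 mg (start 106.5) |
|---|---|---|
| 1 | 81.0 (+1.3%) | 112.5 (-6.2%) |
| 7 | 121.4 (+51.8%) | 136.8 (+14.0%) |
| 28 | 156.9 (+96.1%) | 158.1 (+31.8%) |

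Percentages are relative to the reduced-dose steady state. Averaged over time, with average level = 160 - (160 - start) × (1 - exp(-k d)) / (k d), the excess is smaller: +24.6% (7 days) and +67.9% (28 days) from 80 mg; +3.1% and +20.5% from 120 mg.

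As a share of the 160 mg steady state, the day-28 levels are 156.9/160 = 98.0% and 158.1/160 = 98.8%. The formula approaches 160 from below and never exceeds it. For context, Section 1.2.2 reports: "The maximum tolerated dose was determined to be 240 mg daily".

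**How long the error could run**

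- Visits are 4-weekly (Section 5.4), within 3 days either side (Sections 4.6 and 5.3). At 31 days the levels are about +97% and +32%, so the visit window makes no practical difference.
- Section 8.2.2: "A new pill diary will be provided at every 4 week follow up visit".
- Section 4.4.1.8: "All patients will be seen weekly by their treating radiation oncologist while undergoing EBRT".
- Section 8.2.1: "Unused study drug (enzalutamide) will be documented and returned", though no return interval is stated.
- Supply is 120 capsules of 40 mg at each 4-weekly visit (Section 8.1), so the bottle does not prevent the error. A count would show it. In a 28-day cycle with one missed day there are 27 dosing days, leaving 120 - 4 × 27 = 12 capsules at 160 mg, 120 - 3 × 27 = 39 at 120 mg and 120 - 2 × 27 = 66 at 80 mg.

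These controls limit duration. They do not prevent the first wrong dose.

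**The case against.** The best defence is context. Section 4.1 describes the starting regimen, so its 160 mg can be read as referring to that regimen only. Section 4.2 is devoted to delays and modifications. Its tables already distinguish a current dose from the original starting dose, and no readable row returns anyone to 160 mg. A sensible reader would let the later, more specific rule govern. Table 4.2.1 also uses the term missed doses for held doses, but it states the restart dose in the same cell, so nobody restarting after a hold needs 4.1.

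That defence establishes the likely intent and confines the problem to a forgotten dose in a subject already reduced. It does not remove the problem, because 4.2 is silent on that event and 4.1 gives a specific wrong number for it.

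The caution about size stands. The large figures need a reduction, then a forgotten dose, then 4.1 applied over the assigned dose, then weeks without detection, and the documents give no frequency for any of these steps. A subject recently restarted after a hold may also not be at the assumed steady state. Finally, the contents page lists appendices, and neither these nor the diary's own wording is in the text available, so what subjects are told about missed doses cannot be judged.

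**Conclusion.** The sentence in 4.1 is wrong as written for any subject on a reduced dose and correct for everyone on 160 mg. The severity is minor.

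The error in daily dose is 33% or 100%. Its effect is negligible for a single dose and material only if it persists. Even then, exposure stays within the level planned for every subject at the start. The exposure figures rest on the one-compartment model, the reported half-life and steady state at the reduced dose; the textual conflict does not depend on them.

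The number of subjects at risk is unknown. The documents do not say how many reductions are expected, and planned enrollment is 7 in the Study Summary or ten in Section 10.2. No endpoint definition, sample size or analysis is affected.

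**What to change.** In Section 4.1, replace the fixed 160 mg in the missed-dose sentence with *the subject's currently assigned daily dose (160, 120 or 80 mg)*, and add *doses held for toxicity follow Section 4.2*. The addition also separates a forgotten dose from a held one. If the diary carries missed-dose instructions, check that they say the same.

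The cost is one sentence in the next amendment. Nothing changes for subjects on 160 mg.

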4.2 Toxicities and Dosing Delays/Dose Modifications

Any subject who receives treatment on this protocol will be evaluable for toxicity. Each patient will be assessed for the development of toxicity according to the Time and Events table (Table 5.4). Toxicity will be assessed according to the NCI Common Toxicity Criteria for Adverse Events (CTCAE), version 4.0. Dose adjustments should be made according to the system showing the greatest degree of toxicity.

Enzalutamide (Xtandi, MDV3100) has been shown to be well-tolerated when used in combination with androgen deprivation (in the form of GnRH agonists or castration by orchiectomy) in completed phase I, II, and III clinical trials.

Та	ble 4.2.1 Hematological To	oxicity Dose Reductions for Enzalutamide
ANC	Platelets	Action
≥ 1,500/µL	100,000/μL	None.
1000-1499/μL	75,000-99,000/μL	 -1st Occurrence:Hold current dose until ANC ≥ 1,500/µL and platelets ≥ 100,000/µL. Do not replace missed doses. Restart next treatment at 120 mg dose. -2nd Occurrence:Hold current dose until ANC ≥ 1,500/µL and platelets ≥ 100,000/µL. Do not replace missed doses. Restart next treatment at 80 mg dose. -3rd Occurrence: Discontinue protocol therapy.
500-999/μL	50,000-74,000/μL	 -1st Occurrence:Hold current dose until ANC ≥ 1,500/µL and platelets ≥ 100,000/µL. Do not replace missed doses. Restart next treatment at 120 mg dose. -2nd Occurrence: Discontinue protocol therapy.
<500/μL	<50,000/μL	-1st Occurrence: Discontinue protocol therapy.

Table 4.2.2. Non-hematological Toxicity Dose Reductions		
NCI CTC Grade	Enzalutamide	
0-2	No change from original starting dose (with the exception of seizure)	
3-4	Hold until resolved to	
Second episode of	Hold until resolved to <grade 2,="" 80="" dose<="" mg="" reduce="" td="" then="" to=""></grade>	
grade 3 or 4 toxicity		
Third episode of	Remove subject from trial	
grade 3 or 4 toxicity		

In the randomized clinical trial of patients with docetaxel-refractory metastatic CRPC, 7 of 800 patients (0.9%) treated with enzalutamide 160 mg daily experienced a seizure. No seizures occurred in patients treated with placebo. Patients experiencing seizures were permanently discontinued from therapy and all seizures resolved. There is no clinical trial experience re-administering enzalutamide to patients who experienced seizures. Therefore, should a subject experience any seizure, enzalutamide will be discontinued and the subject removed from the trial.

4.3 Concomitant Medications/Treatments

In vitro studies show that enzalutamide and/or metabolite M2 are potential inhibitors of CYP2C8 and CYP2C19 with lesser potential for inhibitory effects on CYP2B6 and CYP2C9. Enzalutamide is a moderate CYP2C9 and CYP2C19 inducer in humans. For this study, substrates of CYP2B6, CYP2C8, CYP2C9, and CYP2C19 that have a narrow therapeutic index (e.g., paclitaxel, phenytoin, warfarin, omeprazole) are prohibited.

In vitro studies show that enzalutamide is an inducer of CYP3A4. Induction of CYP3A occurs via activation of the nuclear pregnane X receptor (PXR), which is expected to result in co-induction of CYP2C. Co-administration of enzalutamide with CYP3A or CYP2C substrates may reduce oral bioavailability and/or accelerate elimination of these substrates. Enzalutamide is a strong CYP3A4 inducer in humans. For this study, concomitant use of enzalutamide with narrow therapeutic index drugs that are metabolized by CYP3A4 (e.g., alfentanil, cyclosporine, dihydroergotamine, ergotamine, fentanyl, pimozide, quinidine, sirolimus and tacrolimus) is prohibited.

In vitro studies show that enzalutamide is metabolized by CYP2C8 and CYP3A4/5. Strong inhibitors or inducers of these enzymes may affect enzalutamide exposures. Coadministration of a strong CYP2C8 inhibitor (gemfibrozil) increased the composite area under the plasma concentration-time curve (AUC) of enzalutamide plus N-desmethyl enzalutamide in healthy volunteers. For this study, co-administration of enzalutamide and strong CYP2C8 inhibitors (e.g., gemfibrozil) is prohibited. Co-administration of a strong CYP3A4 inhibitor (itraconazole) increased the composite AUC of enzalutamide plus Ndesmethyl enzalutamide by 1.3 fold in healthy volunteers. For this study, strong inhibitors of CYP3A4/5 (e.g., clarithromycin, itraconazole, ketoconazole) are prohibited during enzalutamide treatment.

Use caution when co-administering strong inducers of CYP2C8 (e.g., rifampin) or CYP3A4/5 (e.g., carbamazepine, phenytoin, rifampin, St. John's wort) during enzalutamide treatment, as enzalutamide concentrations may decrease.

In vitro studies show that enzalutamide and metabolite M2 are potential inhibitors of the efflux transporter P-gp. Co-administration of enzalutamide with P-gp substrates may increase the plasma concentrations of the P-gp substrate. Use caution when co-administering sensitive P-gp substrates (e.g., colchicine, dabigatran etexilate, digoxin) during enzalutamide treatment.

Food has no clinically significant effect on the extent of absorption. Enzalutamide may be taken with or without food.

Osteoporosis is a potential adverse effect of GnRH agonist therapy. As per the NCCN Prostate Cancer Guidelines Version 1.2013, screening and treatment for osteoporosis are recommended according to guidelines for the general population provided by the National Osteoporosis Foundation (www.nof.org). It is advised that subjects enrolled in this study be treated for osteoporosis at the discretion of the investigator according to NOF guidelines. These recommendations include treatment with supplemental calcium (1200 mg daily) and vitamin D3 (800-1000 IU daily) for all men > 50 years of age and

additional treatment for men with a 10 year probability of hip fracture \geq 3% or 10 year probability of a major osteoporosis-related fracture \geq 20% as assessed using the FRAX algorithm established by the World Health Organization. Using the FRAX algorithm, GnRH agonist treatment should be considered a secondary osteoporosis risk factor. Osteoporosis reatment options permitted in conjunction with this study for appropriate patients include denosumab 60 mg SQ every 6 months x 6 doses, zoledronic acid 5 mg iv annually, or alendronate 70 mg PO weekly.

Medications known to lower the seizure threshold include but are not limited to:

- Aminophylline/theophylline;
- Atypical antipsychotics (e.g., clozapine, olanzapine, risperidone, ziprasidone);
- Bupropion;
- Lithium;
- Pethidine (meperidine);
- Phenothiazine antipsychotics (e.g., chlorpromazine, mesoridazine, thioridazine);
- Tricyclic and tetracylic antidepressents (e.g., amitriptyline, desipramine, doxepin, imipramine, maprotiline, mirtazapine).

4.4 Other Modalities or Procedures

4.4.1 RADIATION THERAPY

Radiotherapy should begin within 8-10 weeks(+/- 7 days) after the date of the GnRH and enzalutamide administration.injection. Radiotherapy will be administered as standard of care treatment.

4.4.1.1. *Plan 1*: Whole pelvis including prostate and seminal vesicles Acceptable Treatment Modalities:

3D-CRT or IMRT. For patients with N1 disease, only IMRT plan will be allowed.

Prescription Dose (See Table 4.4.1.1):

45 Gy to cover 98% (+/- 3%) of PTV

- Minimum dose within PTV 95% (+/- 5%) of prescribed dose and for a volume that is 0.03 cc
- Maximum dose within the PTV 107% (+/- 3%) of prescribed dose and for a volume that is 0.03 cc

In patients with N1 disease, PTV-N will be defined: Prescription dose (See table 4.4.1.2) 55 Gy to cover 95 % (+/- 5%) of PTV-N

- Minimum dose within PTV 93% (+/- 3%) of prescribed dose and for a volume that is 0.03 cc
- Maximum dose within the PTV 105% (+/- 5%) of prescribed dose and for a volume that is 0.03 cc

Table 4.4.1.1: Radiatio	n Therapy Dose	e Objectives for Plan 1	- Pelvic and Prostate Radiation
-------------------------	----------------	-------------------------	---------------------------------

14,510 11111111	anadon incrapy 20	se objeetres for i mi	11 101/10 4114 1105	tute Huundhon
PTV dose	Minimu	Maximu	Maximum	Maximum
(encompassin	m PTV	m PTV	PTV dose	PTV dose to
g 98% PTV	dose for	dose for a	to a	a volume of
(+/- 3%))	a point	point	volume of	.03 cc of
	with a	with a	.03 cc of	PTV
	volume	volume	PTV	(Deviation
	of .03cc	of .03cc	(variation	unacceptabl
			acceptable	e
)	
45 Gy	42.8 Gy	48.2 Gy	> 48.2-	>49.5 Gy
			49.5 Gy	

*Maximum dose must not be within an organ at risk (OAR) such as the rectum, bladder.

Table 4.4.1.2. Radiation Therapy Dose Objectives for Than 1 – 1 1 V-1						
PTV-N dose	Minimu	Maximu	Maximum	Maximum		
(encompassin	m PTV-	m PTV-N	PTV-N	PTV-N dose		
g 95% PTV	N dose	dose for a	dose to a	to a volume		
(+/- 3%))	for a	point	volume of	of .03 cc of		
	point	with a	.03 cc of	PTV		
	with a	volume	PTV	(Deviation		
	volume	of .03cc	(variation	unacceptabl		
	of .03cc		acceptable	e		
)			
55 Gy	50.06	60.05 Gy	> 57.75-	>60.05 Gy		
	Gv*	-	60.05 Gv	-		

Table 4.4.1.2: Radiation Therapy Dose Objectives for Plan 1 – PTV-N

*if PTV-N is adjacent to small bowel, minimum acceptable PTV-N dose will be dose that can be achieved while meeting absolute small bowel dose constraints.

4.4.1.2. Plan 2: Reduce volume cone down boost plan to the prostate and (proximal) seminal vesicles

Acceptable Treatment Modalities: IMRT or 3DCRT

Table 4.4.2 : Radiation Therapy Dose Objectives for Plan 2 – Prostate and Seminal Vesicle Boost

PTV dose	Minimu	Maximu	Maximum	Maximum
(encompassin	m PTV	m PTV	PTV dose	PTV dose to
g 98% PTV	dose for	dose for a	to a	a volume of
(+/- 3%))	a point	point	volume of	.03 cc of
	with a	with a	.03 cc of	PTV
	volume	volume	PTV	(Deviation
	of .03cc	of .03cc	(variation	unacceptabl
			acceptable	e
)	
34.2 Gy	32.49 Gy	37.62 Gy	> 36.6-	>37.6 Gy
		-	37.6 Gy	

Maximum dose must not be within an OAR such as rectum, or bladder.

